#### 11.2 Reporting

#### **11.2.1** Adverse Events

• Adverse events (AEs) will be recorded from the time of consent until 30 days after treatment discontinuation of study drugs or until a new anti-cancer treatment starts, whichever occurs first.

- AEs will be recorded regardless of whether or not the event(s) are considered related to the study drugs.
- All AEs will be recorded in the subject's medical record and on the appropriate study specific eCRF form within the EDC system.
- All AEs considered related to study drugs will be followed until resolution to ≤ Grade 1 or baseline, deemed clinically insignificant, and/or until a new anti-cancer treatment starts, whichever is earlier.

# **11.2.2 Reporting of Pregnancy**

Although pregnancy is not considered an adverse event, it is the responsibility of investigators or their designees to report any pregnancy or lactation in a subject (spontaneously reported to them), including the pregnancy of a male subject's female partner that occurs during the trial or within 120 days of completing the trial, or 30 days following cessation of treatment if the subject initiates new anticancer therapy, whichever is earlier. All subjects and female partners of male subjects who become pregnant must be followed to the completion/termination of the pregnancy. All pregnancies must be reported within 24 hours to BTCRC AHQ on the BTCRC Pregnancy Reporting form (See Documents/Info tab in the EDC).

Pregnancy outcomes of spontaneous abortion, missed abortion, benign hydatidiform mole, blighted ovum, fetal death, intrauterine death, miscarriage, and stillbirth must be reported as serious events (Important Medical Events). If the pregnancy continues to term, the outcome (health of infant) must also be reported.

Such events must be reported within 24 hours to BTCRC AHQ on the BTCRC Pregnancy Reporting form (See Documents/Info tab in the EDC). BTCRC AHQ will report the event within 24 hours to Pfizer Global Safety (Attn: Worldwide Product Safety; [contact]) and AbbVie ([contact]; [contact]).

# 11.2.3 Site Requirements for Reporting SAEs and Non-Serious Events of Clinical Interest to BTCRC Administrative Headquarters

- SAEs will be reported from time of signed informed consent until 30 days after discontinuation of study drug(s) or until a new anti-cancer treatment starts, whichever occurs first.
- SAEs will be reported on the SAE Submission Form and entered in the SAE tab in the EDC system within 24 hours of discovery of the event.
- SAEs will be reported whether or not they are related to the study drug(s).
- All SAEs will be recorded in the subject's medical record and on the appropriate study specific eCRF form within the EDC system.
- All SAEs regardless of relation to study drug will be followed until resolution to ≤ Grade 1 or baseline and/or deemed clinically insignificant and/or until a new anti-cancer treatment starts, whichever occurs first.
- Non-serious Events of Clinical Interest (including tumor lysis syndrome) will be reported to BTCRC AHQ and will be handled in the same manner as SAEs.
- Additionally, any serious adverse event, considered by an investigator to be related to either study drug, which is brought to the attention of the investigator at any time outside of the 30-day time period specified in the previous paragraph, also must be reported immediately to BTCRC AHQ.

The site will electronically submit the completed BTCRC SAE Submission Form (see Documents/Info tab in the EDC) to BTCRC AHQ within 24 hours of discovery of the event ([contact]). The investigator is responsible for informing the IRB and/or the Regulatory Authority of the SAE as per local requirements.

The original copy of the BTCRC SAE Submission Form and the email correspondence must be kept within the study file at the study site.

Once the SAE has resolved, sites must submit a follow up SAE Submission Form within a reasonable timeframe to BTCRC AHQ electronically to [contact].

#### 11.2.4 BTCRC AHQ Requirements for Reporting SAEs to Pfizer

BTCRC AHQ will submit all SAEs received from sites to Pfizer within 24 hours of receipt of the BTCRC SAE Submission Form and to regulatory authorities (FDA) per federal guidelines.

BTCRC AHQ will submit all SAE reports and any other relevant safety information to:

Pfizer U.S. Clinical Trial Department [contact]

BTCRC AHQ will provide follow-up information to Pfizer as it is received from a site.

#### 11.2.5 BTCRC AHQ Requirements for Reporting SAEs to AbbVie

For any subject receiving Study Product, BTCRC AHQ will submit all SAEs received from sites to AbbVie within 24 hours of receipt of the BTCRC SAE Submission Form and to regulatory authorities (FDA) per federal guidelines.

BTCRC AHQ will submit all SAE reports and any other relevant safety information to AbbVie at: [contact] Email: [contact]

BTCRC AHQ will provide follow-up information to AbbVie as it is received from a site.

#### **11.2.6 BTCRC AHQ Responsibilities for Reporting SAEs to FDA**

BTCRC AHQ has been designated to manage the Investigational New Drug Application (IND) associated with this protocol on behalf of the sponsor-investigator. BTCRC AHQ will cross-reference this submission to Pfizer and AbbVie's parent INDs at the time of submission. Additionally, BTCRC AHQ will submit a copy of these documents to Pfizer and AbbVie at the time of submission to FDA.

BTCRC AHQ will be responsible for all communication with the FDA in accordance with 21CFR312 which includes but is not limited to the 7 and 15 Day Reports, as well as an Annual Progress Report. Additionally, BTCRC AHQ will submit a copy of these reports to Pfizer and AbbVie at the time of submission to FDA.

# 11.3 Sponsor-Investigator Responsibilities

BTCRC AHQ will send a SAE summary to the sponsor-investigator within 1 business day of receipt of SAE Submission Form from a site. The sponsor-investigator will promptly review the SAE summary and assess for expectedness and relatedness.

# 11.4 IND Safety Reports Unrelated to This Trial

AbbVie and Pfizer will provide Big Ten CRC AHQ with IND safety reports from external studies that involve the study drug(s) per their guidelines. Big Ten CRC AHQ will forward the safety reports to the sponsor-investigator who will review these reports and determine if revisions are needed to the protocol or consent. Big Ten CRC AHQ will forward these reports to participating sites **within 1 business day** of receiving the sponsor-investigator's review. Based on the sponsor-investigator's review, applicable changes will be made to the protocol and informed consent document (if required). All IND safety reports will also be made available to sites via the EDC system.

Upon receipt from BTCRC AHQ, site investigators (or designees) are responsible for submitting these safety reports to their respective IRBs, as per their IRB policies.

# **12. STATISTICAL METHODS**

# 12.1 Study Design

This will be a single arm, open-label multicenter study of the combination of Venetoclax and Gemtuzumab Ozogamicin (GO) in patients with relapsed or refractory AML. It will be an initial dose-escalation phase Ib study (Cohorts 1-3), using a 3+3 design to determine whether there is a dose-limiting toxicity. There will be a 28-day induction and then a 28-day consolidation cycle, followed by a maintenance phase.

# 12.2 Endpoints

# **12.2.1 Definition of Primary Endpoint**

- Dose-limiting toxicity, defined as an adverse event related (possible, probably, or definite) to Venetoclax and/or Gemtuzumab fulfilling one of the following criteria:
  - Hematologic toxicity: treatment-related grade 3 or worse neutropenia and/or thrombocytopenia due to bone marrow hypocellularity present at the end of cycle one (day 28) with an additional 28 days allowed for count recovery (i.e. present at day 56); specifically grade 3 or worse neutropenia or thrombocytopenia with the bone marrow documented to be free of leukemic infiltration. Note: patients who enter the study with grade 3 or worse cytopenias will not be evaluable for hematologic dose-limiting toxicities.
  - Non-hematologic toxicity: any grade 3 or worse treatment-related toxicity occurring within the first cycle (excluding grade 3-4 infections during cycle one).

# **12.2.2 Definition of Secondary Endpoints**

- Overall response rate (CR/CRi), as defined by the revised IWG criteria. See Section 9.1.
- Anti-leukemic activity (CR/CRi/PR), as defined by the revised IWG criteria. See Section 9.1.
- Adverse effects will be characterized using the CTCAE v5 criteria.
- Relapse-free survival (RFS), event-free survival (EFS, and overall survival (OS). See Section 9.2

• The European Organization for the Research and Treatment of Cancer 30 item questionnaire (EORTC QLQ-C30), The Functional Assessment of Cancer Therapy Fatigue (FACT-Fatigue) questionnaire, two-minute walk test, and timed chair stands will be performed at trial entry and every other month for 1 year.

# **12.2.3 Definition of Exploratory Endpoints**

- Genomic MRD with droplet digital PCR (ddPCR) will be measured to determine kinetics of response and the association with relapse-free survival at the end of cycles 1 and 2, at 6 months and 12 months, and if there is evidence of relapse. (Sub-PI is [name] [see ref. 33].)
- CD33 DNA polymorphisms will be measured at presentation and at relapse.
- Leukemic blast CD33 expression will be measured at presentation and at relapse.
- "BH3 profiling" of AML blasts will be performed at presentation and at relapse.
- BCL-2, BCL-XL, and MCL-1 protein levels in PB or BM blasts will be measured at presentation and after 6 days (i.e., Cycle 1 Day +3) of Venetoclax therapy

# 12.3 Sample Size and Accrual

A standard "3 + 3" design will be used to establish the maximum tolerated dose. The maximum tolerated dose is defined as the dose level at which fewer than 33% of subjects experience a dose limiting toxicity. An expansion cohort of 6 patients will be carried out at the maximum tolerated dose, which will be the recommended Phase II dose.

This study is a traditional '3 + 3' design without de-escalation, a specified A + B dose finding study with parameters of A = B = 3,  $c_L = 0$ ,  $c_U = 2$ , and  $C_U = 1$ . The associated target quantiles for our study are  $\Gamma_A = 0.35$  and  $\Gamma_A = 0.26$ . Hence, the dose selected by this design has a toxicity rate below 0.26 and above  $C_U/(A + B)$  on average. In simulation studies, the apparent selected dose with our targeted N=18-24 (n=9-18, plus 6) selects a dose with toxicity rate near 0.2. In this scenario, the '3 + 3' design  $\Gamma_U = (C_U + 1)/(A + B) = 2/(3 + 3) = 0.33$  is our upper bound. To evaluate the quality of estimation of the target dose per average sample size increase, we reviewed simulation studies of this design under conditions of A = B = 3 with values of change ( $\Delta$ ) of either 0.35 or 0.70. Within the average sample size range of 16.2 to 21.8, between 78% and 89% correct dose recommendations were achieved, where tendencies of higher  $\Delta$  resulted in greater percent correct dose recommendations [see ref. 45 for further review].

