# PLEASE EMAIL COMPLETED FORM TO BIG TEN CRC ADMINISTRATIVE HEADQUARTERS

# **SYNOPSIS**

TITLE	Phase Ib study of the safety and efficacy of Gemtuzumab Ozogamicin (GO) and Venetoclax in patients with relapsed or refractory CD33+ acute myeloid leukemia					
PHASE	Ib					
OBJECTIVES	Primary Objective: To assess the maximum tolerated dose of Venetoclax when administered with Gemtuzumab Ozogamicin (GO) in patients with AML.					
	Secondary Objectives: To assess the efficacy of this combination in achieving overall response rate (ORR) and anti-leukemic activity; characterize any adverse effects of GO in combination with Venetoclax; and estimate the relapse-free, event-free and overall survival.					
	Exploratory Objectives: To assess the effects of therapy on quality of life; assess genomic minimal residual disease (MRD) to determine the kinetics of response and association with relapse-free survival.					
STUDY DESIGN	Dose-escalation study (Cohorts 1-3) to determine whether there is a dose- limiting toxicity.					
KEY ELIGIBILITY CRITERIA	Eligible patients, 18–75 yrs, will have relapsed/refractory AML, as defined by the World Health Organization classification; ECOG Performance score 0-2; adequate organ function; and do not meet exclusion criteria including WBC >25 × 10  /L (hydroxyurea permitted to decrease WBC count), unresolved ≥grade 2 clinically significant nonhematologic toxicities from prior anticancer therapy or unresolved ≥grade 2 DIC, other active malignancy within 1 year before study entry, major organ dysfunction, active infections, or pregnancy or breastfeeding.					
STATISTICAL CONSIDERATIONS	Standard 3+3 design					
TOTAL NUMBER OF SUBJECTS	N = 15-24 (n = 9-18, plus 6).					
ESTIMATED ENROLLMENT PERIOD	18 months					
ESTIMATED STUDY DURATION	30 months					

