# 5.1 Dose Escalation Rules

- Three to six subjects will initially be enrolled at dose level 1. If none of the 3 subjects experience a dose limiting toxicity (DLT) during the first cycle of therapy, an additional three subjects will be enrolled at dose level 2. If none of the 3 subjects at dose level 2 experience a dose limiting toxicity (DLT), an additional three subjects will be enrolled at dose level 3. If all subjects in dose level 3 complete the first cycle of therapy without DLT, 3 more subjects will be enrolled into dose level 3 to ensure only 0-1 of 6 subjects have a DLT. There will be no further escalation beyond dose level 3.
- Alternatively, if 1 of the first 3 subjects within any given dose cohort experiences a DLT, an additional 3 subjects will be enrolled at that dose level. If only 1 of the total 6 subjects in a dose level experience a DLT, the study will proceed to the next dose level as planned. If 2 of the total 6 subjects in any given dose cohort experience a DLT, the next lower dose level will be explored and considered the maximum tolerated dose (MTD) if no more than 1 of 6 subjects experience a DLT. If this occurs in cohort 1, the dose will be decreased to cohort -1 and if 2 or more DLTs are reached in dose level -1, the study will be put on hold and a protocol amendment will be considered. [see Section 6.4 for "Stopping Rules"]
- The MTD for Venetoclax in combination with Gemtuzumab Ozogamicin is defined as the dose level at which fewer than 33% of subjects experience a dose limiting toxicity (DLT), and specifically is the dose level at which less than 2 out of 6 subjects experience DLT. That dose will be the recommended Phase II dose (RP2D).
- Once the RP2D has been identified, we will expand this cohort to include an additional six patients to further evaluate the efficacy and safety profile of the RP2D.

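### Section 12.3 justifies a 3+3 without de-escalation, while 5.1 and 6.4 de-escalate; its N of 18-24 does not add up, and its 78-89% at average sizes of 16.2-21.8 is not shown to apply to this trial

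*Combined protocol and SAP*

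**What the plan says.** Section 12.3 gives the design as follows: "This study is a traditional '3 + 3' design without de-escalation", an A+B scheme with A = B = 3, c_L = 0, c_U = 2 and C_U = 1. On toxicity it states: "Hence, the dose selected by this design has a toxicity rate below 0.26" and above C_U/(A+B), on average. On accuracy it states: "we reviewed simulation studies of this design under conditions of A = B = 3 with values of change" equal to 0.35 or 0.70, and then: "Within the average sample size range of 16.2 to 21.8, between 78% and 89% correct dose recommendations were achieved". Its sample size is "our targeted N=18-24 (n=9-18, plus 6", closing the bracket. The Synopsis has "N = 15-24 (n = 9-18, plus 6", from the same components.

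The operating rules are elsewhere. Section 5.1: "If 2 of the total 6 subjects in any given dose cohort experience a DLT, the next lower dose level will be explored"; that lower level becomes the MTD if at most 1 of 6 patients has a DLT, and cohort 1 steps down to cohort -1. Section 6.4 repeats this. The table in 5.3 lists four cohorts (-1, 1, 2, 3) of 3-6 patients each. Exclusion criterion 1 foresees a step from cohort 3 back to cohort 2. At the top level, when the first three patients have no DLT, 5.1 adds: "3 more subjects will be enrolled into dose level 3 to ensure only 0-1 of 6 subjects have a DLT".

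**The concern.** Section 12.3 is the only justification of the sample size and of how accurately the MTD, which becomes the RP2D, will be found. If it describes a design other than the one in 5.1 and 6.4, its accuracy figures and its N have no established link to this trial.

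There are three separate problems:

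- The de-escalation label contradicts the rules.
- The lower end of N does not follow from its own parts and differs from the Synopsis.
- The quoted percentages and average sizes come without the settings needed to tell whether they fit three levels plus cohort -1.

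**Working it through.** **1. The plan's own figures.** C_U/(A+B) = 1/6 and (C_U+1)/(A+B) = 2/6 = 0.33 reproduce. The 0.26 is close to the rate at which P(at most 1 DLT in 6) = 0.5, namely 0.264. The 0.35 was not reproduced. The 78-89% cannot be reproduced, because the settings are not given.

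**2. Sample size.** 9+6 = 15 and 18+6 = 24, so the stated components give 15-24. The 9 and 18 are three cohorts of 3 or of 6. That does not match 5.1:

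- With no DLT at all, level 3 still takes six patients: 3+3+6 = 12, or 12+6 = 18 with the expansion.
- A dose-finding total of 9 with a dose selected is possible only if a level is left after 2 or more DLTs in its first three patients, for example 3 at level 1 and 6 at level -1. The total is then 9+6 = 15. If failing cohorts are filled to 6, the minimum is 6+6 = 12, total 18.
- At the upper end, four cohorts of 6 make 24, or 30 with the expansion.

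**3. Two or more DLTs in the first three patients.** In 12.3, c_U = 2 implies leaving the level at once. For cohorts 1-3, sections 5.1 and 6.4 state a consequence only after six patients. Both versions are therefore run below: *immediate* (leave after three) and *filled* (complete to six). Selection probabilities are the same in both; only the sizes differ.

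**4. Exact enumeration under 5.1/6.4.** Start at level 1, put six patients at level 3, fill the lower level to six on stepping down, and make cohort -1 available. The chance of passing a level with DLT rate p on the way up is (1-p)^3[1+3p(1-p)^2]. Level 3 is selected if it is reached and has at most 1 DLT in 6.

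Hand check, scenario E, level 3: 0.990 (p = 0.03) × 0.973 (p = 0.05) × 0.923 (at most 1 of 6 at p = 0.08) = 0.889.

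The DLT rates below are assumptions; the documents give none.

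| Scenario, rates at -1/1/2/3 | Highest dose below 33% selected | Any dose below 33% selected | Mean dose-finding N, immediate / filled | Mean N with expansion |
|---|---|---|---|---|
| A .05/.10/.20/.40 | 45.5% | 85% | 13.1 / 14.1 | 19.0 / 20.1 |
| B .10/.15/.25/.40 | 33.3% | 86% | 12.7 / 13.8 | 18.5 / 19.6 |
| C .05/.10/.20/.30 | 27.0% | 100% | 13.0 / 13.8 | 19.0 / 19.8 |
| D .10/.20/.40/.55 | 49.9% | 79% | 11.7 / 13.2 | 17.5 / 18.9 |
| E .02/.03/.05/.08 | 88.9% | 100% | 12.7 / 12.8 | 18.7 / 18.8 |
| F .02/.04/.07/.12 | 78.9% | 100% | 12.9 / 13.1 | 18.9 / 19.1 |
| G .02/.04/.08/.60 | 87.0% | 96% | 13.1 / 15.0 | 19.1 / 21.0 |

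Totals above 24 have probability at most 0.33% (scenario D).

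**5. Largest possible average size**, by numerical search over all non-decreasing DLT curves:

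| Rules | Dose finding | With expansion |
|---|---|---|
| 5.1/6.4, immediate | 13.6 | 19.6 |
| 5.1/6.4, filled | 15.2 | 21.2 |
| No de-escalation, six at level 3, immediate | 12.4 | 18.3 |
| No de-escalation, six at level 3, filled | 12.5 | 18.4 |
| No de-escalation, three at level 3 if no DLT, immediate | 10.9 | 16.8 |

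The scale is plausible by hand. Failing at level 3 and returning to level 2 costs 3+6+6 = 15 when filled, and each further expansion adds 3 but is unlikely on curves that reach level 3 often. An average of 21.8 exceeds every entry. Even 16.2 exceeds every dose-finding entry, so on this trial's levels it would require counting expansion patients, who enrol after the dose has been chosen.

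**The case against.** Several counter-arguments have weight.

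- *The percentages may be right.* This stands. Section 12.3 defines the MTD by a DLT rate below 33%. If correct means any such dose, the assumed scenarios give 79-100%, at or above the quoted range.
- *The settings may be in the article cited at the end of 12.3.* They may be. What can be said is that the protocol does not state them, apart from a step of 0.35 or 0.70 with no scale. Section 12.3 attributes the average sizes to reviewed simulations, not to a run on this trial's levels; it nevertheless presents them as results for this design.
- *c_U = 2 fills a gap and does not conflict.* Largely so. A level with 2 DLTs in 3 already fails the criterion of fewer than 2 in 6. What stays open is whether three more patients are enrolled, which affects N and not the dose selected.
- *The 18 may be a slip, or the no-DLT total.* Either is possible, but then the n of 9 beside it is wrong.
- *Conduct follows 5.1 and 6.4, whose de-escalation wording agrees, and there is no hypothesis test.* True, and it limits the consequence to the statistical justification.

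A reader might also infer that 78-89% is out of reach because the correct dose has a DLT rate between 1/6 and 0.26. The documents do not support this: 12.3 gives that range as the average rate of the *selected* dose and says nothing about the rate of the correct one.

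**Conclusion.** Two errors stand on the text alone. The de-escalation label in 12.3 contradicts 5.1, 6.4, the 5.3 table and exclusion criterion 1. The N of 18-24 does not follow from 9-18 plus 6, and it differs from the Synopsis.

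A third point rests on calculation: the upper average size of 21.8 cannot describe this trial, whose largest possible average is 21.2 even with failing cohorts filled and the expansion counted. That bound assumes only the 5.1/6.4 rules and DLT rates that do not fall with dose.

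The 78-89% is not shown to apply. It is not shown to be false: across the assumed scenarios the comparable figure is 27-89% for the highest dose below 33%, and 79-100% for any dose below 33%. It would be wrong to infer that a restatement must look less favourable; it may move either way. A very small minimum total should not be inferred either, because that depends on leaving a level after 2 of 3 DLTs, which 5.1 and 6.4 do not state for cohorts 1-3. Totals above 24 are possible but rare.

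**What to change.** - Reconcile 12.3 with 5.1, 6.4 and exclusion criterion 1 on de-escalation, and on what follows 2 or more DLTs in the first three patients. Which rule applies is for the sponsor to settle.
- State one N in 12.3 and the Synopsis that follows from the reconciled rules, including six patients at level 3 and cohort -1, and note the rare paths outside the range.
- Remove the sentence with 78-89% and 16.2-21.8, or label it as results from other simulated settings and state those settings.
- In its place, define correct and report exact operating characteristics of the reconciled rules under a few stated DLT scenarios, at least one with a safe top dose. Give the selection probability per level, expected N with and without the expansion, and the chance of selecting a dose with a DLT rate of 33% or more.

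The cost is text and a short calculation. The restatement needs no extra patients.

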# 12.4 Assessment of Safety

Patients evaluable for toxicity are those who receive at least one dose of Venetoclax and one dose of GO. The NCI Common Terminology Criteria for Adverse Events (CTCAE) v5 will be used to grade adverse events per the defined Study Calendar for toxicity assessment schedule.

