# 2.2 Endpoints

# 2.2.1 Primary Endpoint

- Dose-limiting toxicity, defined as an adverse event related (possible, probably, or definite) to Venetoclax and/or Gemtuzumab fulfilling one of the following criteria:
  - Hematologic toxicity: treatment-related grade 3 or worse neutropenia and/or thrombocytopenia due to bone marrow hypocellularity present at the end of cycle one (day 28) with an additional 28 days allowed for count recovery (i.e. present at day 56); specifically grade 3 or worse neutropenia or thrombocytopenia with the bone marrow documented to be free of leukemic infiltration. Note: patients who enter the study with grade 3 or worse cytopenias will not be evaluable for hematologic dose-limiting toxicities.
  - Non-hematologic toxicity: any grade 3 or worse treatment-related toxicity occurring within the first cycle (excluding grade 3-4 infections during cycle one).

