# 5.2 Definition of Dose-limiting Toxicities

Dose-limiting toxicities (DLTs) are defined as an adverse event related (possible, probable or definite) to Venetoclax and/or Gemtuzumab Ozogamicin fulfilling one of the following criteria:

 Hematologic toxicity: treatment-related grade 3 or worse neutropenia and/or thrombocytopenia due to bone marrow hypocellularity present at the end of cycle one (day 28) with an additional 28 days allowed for count recovery (i.e. present at day 56); specifically grade 3 or worse neutropenia or thrombocytopenia with the bone marrow documented to be free of leukemic infiltration. Note: patients who enter the study with grade 3 or worse cytopenias will not be evaluable for hematologic dose-limiting toxicities.

• Non-hematologic toxicity: any grade 3 or worse treatment-related toxicity occurring within the first cycle (excluding grade 3-4 infections during cycle one).

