# NOTE: Events that can be clearly attributed to disease progression, concurrent illness or the effects of other medications will not be classified as DLTs.

DLTs will be counted based on the number of patients with a DLT at a given dose level, not the absolute number of DLTs. No single patient can trigger more than one DLT. Intra-patient dose escalation is not permitted.

Cohort	Number of Subjects	Venetoclax Daily Dose (mg)	Gemtuzumab Ozogamicin IV on Days +1, +4, +7
-1	3-6	100	
1 (start)	3-6	200	$3 \text{ mg/m}^2$
2	3-6	400	(up to one 4.5 mg vial)
3	3-6	600	

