# 5.3 Dose Cohorts

# 5.4 Induction (Cycle 1) and Consolidation (Cycle 2):

Cycle 1: Gemtuzumab Ozogamicin (GO) 3 mg/m^2 IV infusion (up to one 4.5 mg vial) will be given on days +1, +4, and +7 in combination with daily oral administration of Venetoclax during Induction. Based on previous studies, Venetoclax dose will start at 200 mg daily with dose escalation planned over 3 cohorts to identify the recommended phase 2 dose (RP2D). Dose cohort 3 will use the maximum dose of Venetoclax of 600 mg orally daily. Because of evidence of tumor lysis syndrome (TLS) with Venetoclax use in previous CLL studies, we will use a 3-day stepwise ramp up in cycle 1 to the target dose for all cohorts (see Table 1). Patients should expect to be hospitalized throughout Induction/Cycle 1, although medically stable patients may be discharged from the hospital under close supervision at the discretion of the treating physician. Patients do not have to be hospitalized during the first week of consolidation if the treating physician wishes to administer Gemtuzumab (C2D1 and D4) in the outpatient clinic.

Day	Cohort 1 (mg)	Cohort 2 (mg)	Cohort 3 (mg)
-2	50	50	100
-1	100	100	200
0	100	200	400
1–28	200	400	600

Table 1. Venetoclax Ramp-up schedule

Clinical and hematological responses will be assessed after the end of both the induction and consolidation cycles. Bone marrow assessment will occur on day 28 regardless of absolute neutrophil count (ANC) or platelet recovery.

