# Table 2. Induction (Cycle 1) and Consolidation (Cycle 2) Venetoclax and Gemtuzumab Administration

Drug	Dose 	Route	Schedule	Cycle Length
Venetoclax 	Assigned dose 	Orally	Days 1-28 (Cycle 1: Day -2, -1, 0) 	
Gemtuzumab	$3 \text{ mg/m}^2$	Infusion	Cycle 1 : Days 1, 4, and 7	28 days
	(up to one 4.5 mg vial)		Cycle 2 : Days 1, 4	

Body surface area (BSA) should be recalculated when weight changes by  $\ge 10\%$  according to the Mosteller formula.

Please see Table 1 stepwise ramp-up schema

Venetoclax tablets should be taken orally once daily with a meal and water. Do not chew, crush or break tablets. **NOTE:** Diaries will be provided for self-administration of Venetoclax when subjects are outpatient. On days when both venetoclax and gemtuzumab are given, it is preferred that subjects take venetoclax 1 hour prior to the GO infusion. However, variations from this guidance will not be considered as protocol deviations.

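### The 12.4 toxicity-evaluable set leaves out patients given only ramp-up venetoclax, the DLT window is stated in conflicting ways, and no DLT-evaluable set covers treated patients who leave unobserved

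*Combined protocol and SAP*

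**What the plan says.** **Toxicity set.** Section 12.4: "Patients evaluable for toxicity are those who receive at least one dose of Venetoclax and one dose of GO". Section 5.4 describes a "3-day stepwise ramp up in cycle 1 to the target dose for all cohorts", and Table 2 gives the venetoclax schedule as "Days 1-28 (Cycle 1: Day -2, -1, 0". GO is first given on Day 1.

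**DLT definition.** Sections 2.2.1 and 12.2.1 define a DLT as "an adverse event related (possible, probably, or definite) to Venetoclax and/or Gemtuzumab fulfilling one of the following criteria"; 5.2 is equivalent. The non-hematologic criterion in 5.2 is "any grade 3 or worse treatment-related toxicity occurring within the first cycle (excluding grade 3-4 infections during cycle one". On counting, 5.2 says "DLTs will be counted based on the number of patients with a DLT at a given dose level". It also says "Events that can be clearly attributed to disease progression, concurrent illness or the effects of other medications will not be classified as DLTs".

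**Evaluability for DLT.** The only statement is in the DLT definition: "patients who enter the study with grade 3 or worse cytopenias will not be evaluable for hematologic dose-limiting toxicities". Section 12.6.1 presents DLTs by venetoclax dose and names no analysis set.

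**Replacement.** Section 4 replaces registered patients who cannot begin treatment. Those who begin and then stop are to be followed under 7.2, with no mention of replacement.

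**Window.** Section 6.1.2 gives non-hematologic DLTs a window of the first 56 days and excludes only grade 4 infections. Section 6.1.1 places hematologic DLTs after day 56, where 5.2 has them present at day 56. Section 6.4 monitors DLTs to Day 56.

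**The concern.** DLT is the sole primary endpoint, and each escalation decision rests on 3 or 6 patients, so the classification of one patient can change the decision.

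Three things do not fit together. First, the only toxicity population in the plan requires both drugs, while the primary endpoint can be met on venetoclax alone during the three days before GO. The efficacy set in 12.5 needs only one dose of study drug, so the toxicity set asks for more drug exposure than the efficacy set does. Second, a patient cannot be said to have been observed through the DLT window while the window has two lengths for one component and two timings for the other. Third, nothing says how much exposure or observation makes a patient DLT-free. Sections 5.6 and 6.3 allow exit for transplant, progression, patient request or physician decision. If an unobserved leaver is counted as DLT-free, the observed DLT rate can only go down, which favours escalation. Without a rule, the choice would be made case by case in an open-label study with outcomes already known.

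**Working it through.** **1. Ramp-up patient, section by section.** Suppose a venetoclax-related grade 3 or worse non-hematologic event, not an excluded infection, occurs on Day -1 and GO is never given.
- 5.4 places the ramp-up in cycle 1, so the event is inside the first cycle.
- 2.2.1, 5.2 and 12.2.1 accept attribution to either drug, so it is a DLT.
- 5.1, 5.2 and 6.4 count patients with a DLT and do not mention 12.4, so it counts for escalation.
- 12.4 requires a GO dose, so the patient is not toxicity-evaluable.
- 11.2.1 records AEs from consent, so the event is captured.

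The conflict is in the denominator, not in data collection.

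**2. The window.**

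| Component | 5.2 (also 2.2.1, 12.2.1) | 6.1 |
|---|---|---|
| Non-hematologic, period | first cycle | first 56 days |
| Non-hematologic, infections excluded | grade 3-4 | grade 4 |
| Hematologic, timing | present at day 56 | after day 56 |

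An event meeting the hematologic wording of 6.1.1 would also fall after the monitoring limit in 6.4.

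**3. Who is unobserved.** Section 7.1 requires a safety visit 30 days (±7) after the last dose, whatever the reason for stopping. Section 11.2.1 records AEs for 30 days after stopping or until new anti-cancer treatment.
- Earliest possible last dose: Day -2 + 30 = Day 28, the end of the cycle.
- To reach Day 56 by the same rule, the last dose must be on Day 56 - 30 = Day 26 or later.

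So the 28-day window is covered for most leavers. The gap is mainly those who start new therapy or withdraw from the study, and observation to day 56.

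**4. Size at levels 1 and 2.** The plan's own figures reproduce: 9 + 6 = 15 and 18 + 6 = 24 (synopsis), and an upper bound of 2/6 = 0.33 (12.3).

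Under 5.1 a level is passed with 0 of 3, or with 1 of 3 followed by 0 of the next 3:

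P(escalate) = (1-p)³ + 3p(1-p)⁵

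At p = 0.33: 0.67³ + 3(0.33)(0.67⁵) = 0.301 + 0.134 = 0.434.

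Let a fraction m be wholly unobserved and counted as DLT-free. The apparent rate is p(1-m):
- m = 0.10: 0.33 × 0.90 = 0.297, giving 0.500
- m = 0.20: 0.33 × 0.80 = 0.264, giving 0.570

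If half of a leaver's DLT chance is still observed, the apparent rate is p(1-m/2):
- m = 0.10: 0.3135, giving 0.467
- m = 0.20: 0.297, giving 0.500

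Other true rates, wholly unobserved case:

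| True DLT rate | m = 0 | m = 0.10 | m = 0.20 |
|---|---|---|---|
| 0.20 | 0.709 | 0.752 | 0.793 |
| 0.26 | 0.578 | 0.635 | 0.691 |
| 0.33 | 0.434 | 0.500 | 0.570 |
| 0.40 | 0.309 | 0.378 | 0.454 |

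The chance that a cohort of 3 contains at least one such leaver is 1 - (1-m)³ = 0.271 or 0.488. The documents give no exit rate; both values of m are assumptions.

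**5. Replacements.** If all 18 escalation slots are used, the expected number of extra patients is 18m/(1-m) = 2.0 at m = 0.10 and 4.5 at m = 0.20.

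**The case against.** The strongest reply is that follow-up already closes most of the gap. The 30-day visit and AE recording reach Day 28 even for a patient who stops on the first ramp-up day. Transplant is a weak exit route in cycle 1, because 5.6 suggests 2-3 months between the last GO dose and conditioning. A patient who leaves with leukemia in the marrow does not meet the hematologic criterion, which requires a marrow free of it. All of this stands, and it is why the escalation figures are an upper bound.

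On 12.4, the reply is that 12.6.2 reports all adverse effects and the worst-grade tables in 12.6.3 are not said to be confined to evaluable patients, while 12.6.3 discloses the number evaluable. This also stands: only analyses that actually use the 12.4 denominator lose the patient.

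A reader might infer three stronger things. One is that 12.4 removes ramp-up DLTs from escalation decisions; it does not say so, and 5.1, 5.2 and 6.4 count them. Another is that every early leaver goes unobserved; 7.1 and 11.2.1 contradict that. The third is that level 3 has the same bias. There, 5.1 adds the second three patients once all subjects complete cycle 1 without a DLT, and a leaver among the first three does not meet that condition. No level 3 figure is offered. The silence of 5.1 on a window at level 2 also carries little weight, since the DLT definition supplies one.

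The reply does not supply an evaluability rule, a replacement rule for treated patients, or a single window.

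**Conclusion.** The point holds in this limited form and should be fixed. The 12.4 set excludes patients whose events the primary endpoint includes; the effect is on the toxicity denominator, not on escalation, provided 5.1 and 5.2 govern counting. The window and infection exclusion contradict each other within the document and must be reconciled. A treated patient who leaves unobserved can count as DLT-free at levels 1 and 2, which biases toward escalation. At a true rate of 0.33 the rise is at most from 43% to 50% or 57%, assuming 10% or 20% wholly unobserved, and to 47% or 50% if half of each leaver's risk is seen. The direction follows from the rules as written; the size rests on assumed exit rates. Nothing here shows that such a bias has occurred.

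**What to change.** (a) In 12.4, define the safety set as all patients with at least one dose of either study drug. State that every event meeting the DLT definition, including one before GO, counts in 5.1 and is presented under 12.6.1.

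(b) Reconcile the DLT window and the infection exclusion across 2.2.1, 5.2, 6.1, 6.4 and 12.2.1. Which version applies is for the sponsor to choose. This must come before (c).

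(c) In 5.1, 12.4 and Section 4, define the DLT-evaluable set as patients with a DLT, plus patients without one who received a sponsor-specified minimum exposure to both drugs and were observed through the reconciled window. Do not count other patients as DLT-free; replace them. The exposure condition is needed: with observation alone, a patient who never received GO could count as DLT-free for the combination.

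(d) Report hematologic DLTs with the number evaluable for that component.

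The cost is wording, possibly a few replacement patients with added accrual time, and a reported DLT rate that may look less favourable. The stated maximum of 24 may need restating: on the assumed rates of 10% or 20%, the upper-bound expectation is 24 + 2 = 26 or 24 + 4.5 = 28.5 patients, and fewer if most leavers are observed.
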